2.1.3 Maternal and Newborn Health in Chad

Chad continues to face challenges with high mortality rates and poor outcomes in maternal and child health. Establishing a baseline of information on the availability and quality of care offered in healthcare facilities across the country was therefore a key priority for the government to ensure better understanding of the current situation and to identify gaps which need to be addressed in order to ensure strategic action is taken to improve health care and healthcare outcomes during and after pregnancy.

Uptake of antenatal and postnatal care is relatively limited: six out of ten women attend / complete at least one ANC visit and the proportion falls to three out of ten for four visits prenatally, compared to 86% and 62% globally. Postnatally, the statistics are even less adequate, with 16% of mothers and under 5% of babies receiving a postnatal visit within the first 48 hours of delivery (INSEED, 2016).

Just one in five deliveries are conducted in healthcare facilities and a quarter are assisted by a skilled birth attendant (INSEED, 2016) indicating limited engagement with more formal health services. The number of maternal deaths per 100,000 live births (maternal mortality ratio) is estimated to be 856, placing Chad in the 227th position of 229 countries globally. For newborn mortality, Chad ranks 221st of 225 countries globally based on 2017 statistics (World Bank, 2020). This suggests that there are considerable gaps with regard to care for women and babies, which require concerted effort to improve availability but also quality of care, a determinant that has been widely identified for preventing mortality and morbidity among mothers and newborns (WHO, 2013).

Table 1: Maternal health indicators in Chad

Indicator	Value
AN care – at least 1 visit (%) *	62.5
AN care – 4+ visits (%) *	31.0
PNC visit within 2 days for baby (% of all births) *	4.5
PNC visit within 2 days for mother (% of all births) *	16.0
Births in health care facilities (%) *	21.7

Indicator	Value
Births attended by skilled personnel (%) ** (2010)	24.3
Maternal mortality ratio (per 100,000 live births) ** (2015)	856
Neonatal mortality rate (NMR), deaths per 1,000 live births*** (2018)	34.2

^{*}Source: DHS-2014-15 (INSEED, 2015)

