3.1.2 Selection of participating women

All women aged 18 years-old or more coming for an ANC or PNC visit will be eligible to be included in the trial and the care they receive observed. Exclusion criteria include:

- Age less than 18 years-old
- Refusal of client for her care to be observed to the study

 Any expression of physical or psychological distress under the idea of being observed during consultation while receiving information

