involve multiple components, at least one of which is always applicable; some components are only applicable to a subset of clients, eg HCP counsels the woman about mental health is only applicable if the client's response to a previous question is cause for concern. All essential components will carry a weight of 1. The overall score will be derived by aggregating the weighted scores for each essential component which will then be converted to a percentage. Six essential components are binary; hence the score can only be 0 (not achieved), or 1 (achieved and single weighted); in some cases the determination of this involves an algorithm. The other seven essential components are not binary as they have sub-components assessed independently and thus may be partially achieved and carry an intermediate score, eg a multiple of 0.25 for essential component 1 (respectful maternal care).

Outcome 2: Essential components included in the composite measure of integrated services specific to PNC visits are listed below.

- EC1b = Respectful maternity care indicators:
 - Introductions, greeting the woman, consent, questions
- EC2b = Screening for Pre-eclampsia:
 - Measure BP
- EC3b = Screening for, prevention and management of Anaemia:
 - Measure Haemoglobin
 - Provide ferrous sulphate with folic acid
- EC4b = Screening for, prevention and management of Malaria:
 - Checked for clinical symptoms and test for Malaria if relevant
 - Provide bed nets if not provided yet
- EC5b = Screening for, prevention and management of HIV:
 - Test for HIV
 - Provide Prevention of mother to child transmission care (PMTCT)
 - Provide anti-retroviral drugs (ARV) for mother and baby
- EC6b = Screening for, prevention and management of Syphilis:
 - Test for syphilis
 - Provide antibiotics if needed
- EC7b = Screening for, prevention and management of Tuberculosis (TB):
 - Checked for clinical symptoms and test for TB
 - First line TB drugs or referral if needed
- EC8b = Prevention of Tetanus in mother and baby:
 - Tetanus toxoid vaccination
- EC9b = Screening and counselling for mental health and domestic violence:
 - Screening tools
 - Counselling services
- EC10b = Provide advice and support regarding breastfeeding:
 - Consultation

- EC11b = Offer postpartum contraception:
 - Consultation
- EC12b = Monitor newborn growth:
 - Weigh the baby
- EC13b = Clinical examination of the mother:
 - Examine the mother
- EC14b = Clinical examination of the baby:
 - Examine the baby

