- EC15b = Immunization status checked and required vaccinations offered and provided if required
- EC16b = Provide advice on danger signs in the mother and baby:
 - Consultation

The outcome for each PNC visit will be a score which measures the proportion of the above components that was delivered during that visit (EC_PNC). This score will be derived in a similar manner to the score for ANC, the difference being that three essential components used for ANC will be dropped and six others added.

The observation tool is detailed in **Appendix 2**.

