The consenting process for the healthcare facility manager will cover all elements of the trial, including details and organisation of the intervention and the required inputs concerning the conduct of the trial and data collection processes. Once explained, opportunities to familiarise with the trial information, ask questions and seek further clarifications as needed will be encouraged. In-country and LSTM staff will be on stand-by to address any queries and provide details as needed. The facility in-charge (or another relevant member of the leadership team) will be asked to provide consent on behalf of the healthcare facility. The data collection processes and details will be explained and discussed in detail as part of visits conducted to each of the HCF by the study team. The stepped-wedge calendar will be explained to them and at least 1 week before the beginning of each step, the study team will contact the facility that will have ANC-PNC observed to plan for the data collector's visit. No observation will be conducted unexpectedly, and data collectors will work based on the staff roster to ensure the participating healthcare providers are observed.

The confidentiality and privacy of the observed facility staff, as well as patients will be stressed. It will also be explained that the data collection, while centring around care provided, will not collect any non-anonymised details from patients. All involved will receive all information detailing the purpose of the assessment, what is involved, and that the research team will be available to answer any questions.

Consent from healthcare providers will be sought before the launch of the trial, then refreshed before conducting each day of observation, and consent from clients before asking for inputs each visit observed. Each day of observation, the information about the study will be shared with each participating healthcare provider.

Clients will be women who receive antenatal or postnatal care either/both for themselves or/and their baby. The purpose of the data collection will be explained by the data collector both to the HCP and the client, including the type of information that will be collected, as well

as the voluntary nature of their participation. It will be reiterated that participant confidentiality and anonymity will be upheld.

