Appendix 2: Tools for data collection for observation

Below is the observation checklist. Essential components are numbered slightly differently than appendix 1 for the construction of the score. The scoring attributes will not appear for the data collectors and only be used by the statistician at time of analysis. Each essential component is score 1, for a total of 13 essential components for ANC visits, and 16 for PNC visits. Essential components can be a sum of x number of subcomponents as indicated in the table. Each subcomponent needs all applicable questions to be observed (Please see examples of algorithms at the end of appendix).

Please note this tool is to be deployed on an electronic platform, therefore the formatting of the tool will be visually different to what is included here. All boxes starting with "If" will only appear depending on the answer to the relevant condition (e.g. treatment will only be asked for women tested positive). The "Not applicable" answer is available for questions which depend on the gestational age and type of visit. The tool will be deployed in FRENCH.

OBSERVATION

Variable label	Answers	Conditionality	Scoring
GENERAL			
Please select the region	[dropdown menu]		
Please select the name of the facility	[dropdown menu]		
If 'Other' facility, please specify	[free text]		
Date of survey	[select from calendar]		
Name of person completing form	[free text]		
Anonymous ID of HCP	[free text]		
ANC			
ANC general information			
First/subsequent contact	0 - Subsequent contact, 1 - first contact -99 INF		
Which subsequent visit was it?	2- ANC2, 3- ANC3, 4- ANC4, 5- ANC5, 6-ANC6, 7- ANC7, 7-ANC8	Only to appear if previous answer = 0 – Subsequent visit	
Gestational age (weeks)	[integer]		
Who gave information about gestational age	1 - Woman, 2 - Healthcare provider, 3 - Other (specify)		
If other, specify	[free text]		
Women arrival time in the facility	[time]		
Comments	[free text]		

ANC contact		
EC1: Respectful maternity		1 (sum of all
care		subcomponents)
RMC subcomponent 1		0.25 (Points given if all applicable questions are observed)
The healthcare provider		
(HCP) introduced		
themselves to the		
pregnant woman	0 - No, 1 - Yes	
The HCP greeted the		
pregnant woman (or		
answered if woman		
greeted first)	0 - No, 1 – Yes	
RMC subcomponent 2		 0.25
The HCP asked the		
pregnant woman to take a	0 - No, 1 - Yes, -88 - Not	
seat	applicable (no chairs)	
The HCP asked the		
pregnant woman if she		
came with a companion		

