HCP checked the perineum	0 - No, 1 - Yes	
to look for scar of any	,	
perineal tear and/or		
episiotomy performed		
HCP checked the abdomen	0 - No, 1 - Yes	
to see if any wound from	,	
caesarean section		
HCP recognised and acted	0 - No, 1 - Yes, -88 - Not	
upon abnormal findings	applicable (no abnormal	
with abdominal or	findings)	
perineum examination		
Mother exam		0.5
Subcomponent 3		
HCP asked about urination	0 - No, 1 - Yes	
and urinary continence		
HCP asked about bowel	0 - No, 1 - Yes	
function		
HCP asked the woman	0 - No, 1 - Yes	
about signs of Deep vein	0 110, 1 100	
thrombosis in her legs		
HCP gave the woman	0 - No, 1 - Yes	
hygiene advice	,	
HCP recognised and acted	0 - No, 1 - Yes, -88 - Not	
upon abnormal findings	applicable	
EC14b = Clinical		1
examination of the baby		
HCP observed hygiene	0 - No, 1 - Yes	
measures before		
examining the baby		

Have the newborn's eyes	0 - No, 1 - Yes	1	 
been checked?	0 - 100, 1 - 163		
Was the temperature of	0 - No, 1 - Yes		
the newborn taken with a	0 - 100, 1 - 163		
thermometer?			
Has the HCP listened to	0 - No, 1 - Yes		
the heartbeat of the	0 - 100, 1 - 163		
newborn (auscultation)?			
Did the HCP examine the	0 - No, 1 - Yes		
abdomen of the newborn	0 - 100, 1 - 163		
(palpation)?			
Has the HCP checked the	0 - No, 1 - Yes		
umbilical cord of the	0 140, 1 163		
newborn?			
Has the HCP checked if the	0 - No, 1 - Yes		
newborn is passing urine	1, 2		
Has the HCP checked if	0 - No, 1 - Yes		
the newborn has passed	1, 2		
stools or opened its			
bowel?			
Has the newborn been	0 - No, 1 - Yes		
weighed?			
HCP completed the baby's			
growth chart			
	0 - No, 1 - Yes, -88 - Not		
HCP recognised and acted	applicable (no abnormal		
upon abnormal findings	findings)		
EC15b = Immunization			1
status checked and			
required vaccinations			
offered and provided			
HCP checked whether	0 - No, 1 - Yes		
newborn vaccines are up-			
to-date			
HCP offered appropriate	0 - No, 1 – Yes, -88 Not		
vaccination	applicable		
EC16b = Provide advice on			1
danger signs in the			
mother and baby			
HCP gave advice on	0 - No, 1 - Yes		
danger signs (i.e. signs that			
indicate the baby is sick) to			
look out for in the baby			
HCP gave the date of the	0 - No, 1 - Yes	Does not	
next PNC contact to the		appear if PNC	
mother		visit = W6	
Woman departure/exit	[enter time]		
time			
Comments	[free text]		

SCORING EXAMPLE: Respectful Maternity Care essential component

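### The PNC score counts baby components at every visit, although eligibility does not require a living or present baby and the visible form cannot record that they do not apply

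*Protocol*

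**What the plan says.** **Who is observed.** Section 3.1.2: "All women aged 18 years-old or more coming for an ANC or PNC visit will be eligible to be included in the trial". The exclusions are age under 18, refusal, and distress at being observed; none concerns the baby. Section 3.5.3 describes the clients: "Clients will be women who receive antenatal or postnatal care either/both for themselves or/and their baby".

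**How a visit is scored.** Appendix 2: "Each essential component is score 1, for a total of 13 essential components for ANC visits, and 16 for PNC visits". Section 3.4 agrees: "All essential components will carry a weight of 1". It builds the PNC score from the ANC score, "the difference being that three essential components used for ANC will be dropped and six others added". For ANC, section 3.4 states that all thirteen components are applicable, and that a component with several parts always has at least one part that applies. It makes no such statement for PNC.

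**When an item may be skipped.** The introduction to Appendix 2 ties the not-applicable answer (-88) to gestational age and type of visit. PNC visit type is coded only as under 48 hours, day 6 or week 6.

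**The baby rows that can be seen.** The EC14b examination rows, such as the one beginning "Have the newborn's eyes", offer yes or no; only the row on acting upon abnormal findings offers -88. In EC15b the vaccine-status check is yes/no, while the offer of vaccination has -88. In EC16b the advice on danger signs in the baby is yes/no.

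**The concern.** The eligibility text admits mothers who come without their baby, and mothers whose baby was stillborn or has died. For them some of the 16 components cannot be delivered, however well the provider works. The form then leaves the observer two choices: enter 0, or leave the row blank. A 0 treats impossible care as failed care. A blank may remove the visit, because section 3.8 omits data when the outcome is missing.

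PNC delivery is one of two primary outcomes. Visits with a lower ceiling cannot show the full effect of training, and their number will vary by chance, with about four PNC visits per provider per assessment period. For a bereaved mother, the score would count it against the provider that no baby was examined. Because no visible row records the baby's status, an analyst could not later tell omitted care from inapplicable care. That is why this cannot simply be left to the analysis stage.

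**Working it through.** **1. Reproduce the 16.** The section 3.4 rule gives 13 − 3 + 6 = 16. The list EC1b to EC16b also has 16 entries. The stated total holds.

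**2. Which components are lost** (section 3.4 numbering). Appendix 2 gives credit only when all applicable questions are observed. EC14b, EC15b and EC16b show no subcomponents, so each is earned or lost whole.

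- *Baby alive but absent.* EC14b is lost. EC12b (newborn growth) is lost too if its rows have no -88. EC15b is not necessarily lost: vaccine status can be checked with the mother, and the offer row has -88. Breastfeeding and danger-sign advice can also still be given.
- *Baby stillborn or died.* EC14b, EC15b and EC16b are lost on the visible rows. EC10b (breastfeeding) and EC12b may be lost as well.

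The rows for EC10b and EC12b are missing from the text available to this review, so they are counted only as possible losses.

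**3. Ceiling = (16 − lost components) / 16.**

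| Visit | Lost | Ceiling |
|---|---|---|
| Baby alive, absent: EC14b only | 1 | 15/16 = 93.8% |
| Baby alive, absent: EC14b and EC12b | 2 | 14/16 = 87.5% |
| Bereaved: visible rows | 3 | 13/16 = 81.3% |
| Bereaved: plus EC10b and EC12b | 5 | 11/16 = 68.8% |

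With a denominator of applicable components, every ceiling would be 100%.

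**4. Attenuation.** Assume a share f of visits loses k components, f is the same before and after training, and training acts equally on all components. The effect then shrinks by the fraction f × k/16. The protocol gives no f; 10% and 30% are assumptions, here for a living but absent baby.

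- k = 2: 0.10 × 2/16 = 1.25%; 0.30 × 2/16 = 3.75%.
- k = 1: 0.10 × 1/16 = 0.6%; 0.30 × 1/16 = 1.9%.

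The stated detectable difference is 0.81 × √(0.01 + 0.0675) = 0.81 × 0.278 = 0.225, which the protocol gives as 0.23. A shrinkage of 1.25% to 3.75% of 0.23 is 0.003 to 0.009.

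**5. Noise.** At the protocol's assumed 50% delivery, two lost components lower a visit's score by 0.5 × 2/16 = 0.0625. The added standard deviation is 0.0625 × √(f(1 − f)): 0.019 at 10% and 0.029 at 30%. Combined with the assumed visit-level limit of 0.2, this gives √(0.04 + 0.019²) = 0.201 and √(0.04 + 0.029²) = 0.202.

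**6. Bias if the share shifts.** If the share of such visits differed by 20 points (assumed) before and after training, the estimate would move by 0.20 × 0.0625 = 0.0125. That is about 5% of 0.23, and 12.5% of the 0.1 effect used in the protocol's simulations.

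**The case against.** The strongest reply is that no sentence assigns 0 to an absent baby. Appendix 2 speaks of applicable questions and refers to scoring algorithms, of which only a heading is available here. Section 3.4 says some items apply only to some clients. The form also uses -88 more widely than its introduction suggests, for example when there is no companion. Detailed handling of inapplicable items often belongs in a statistical analysis plan.

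Part of this stands: the sponsor may intend such visits to be excused. But the rule on applicable questions governs credit within a component and does not alter the stated total of 16. The visible EC14b examination rows have no -88, and an analysis plan cannot recover a baby status that was never recorded.

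A reader might infer more than the documents support:

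- *That 72% of visits have no baby.* Table 1 gives early PNC visits for 16.0% of mothers and 4.5% of babies, and 1 − 4.5/16.0 = 0.72. These are national coverage figures for the first two days. They do not say whether the baby came, and a baby present but not checked produces the same gap.
- *That neonatal mortality (34.2 per 1,000 live births) is a lower bound.* Deaths may follow the visit, and bereaved mothers may attend less often.
- *That visits for the baby only have the same defect.* The mother is there, and the lay summary describes care for both in one visit, so a 0 for not examining her may be intended.
- *That the training effect is biased.* That needs a share that changes with training, for which the protocol gives no evidence.

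**Conclusion.** The point holds as an inconsistency between eligibility, form and score. Visits without a living or present baby are admitted, scored out of 16, and recorded on rows that, where visible, cannot show that the care did not apply. The individual scores can be well off: ceilings of 87.5% to 93.8% with a living but absent baby, and 68.8% to 81.3% for a bereaved mother. The lower figure in each range depends on form rows not seen here.

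The effect on the trial estimate is probably small: about 1.3% or 3.8% relative attenuation if 10% or 30% of visits had a living but absent baby and lost two components, with little added noise. These figures rest on assumed shares and on equal training effects across components. The case for acting is that a primary outcome would mix failed and inapplicable care, that the two could not be separated afterwards, and that prevention is cheap.

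**What to change.** Before data collection:

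1. Add one row at the start of the PNC form for baby status: present; alive but absent; died or stillborn.
2. Use that row to code as -88 the baby items that cannot apply, and list in the scoring algorithm which items these are under each status. EC16b needs its own rule: without its baby row it rests on the next-contact row, which does not appear at week 6.
3. Compute EC_PNC as points divided by applicable components, and state this in section 3.4 and Appendix 2 in place of the fixed 16.
4. Add a sensitivity analysis in which a living but absent baby's components count as not delivered, since absence may itself reflect how care is organised.

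The cost is one form row, a skip rule, a line of scoring code and one extra analysis. The small drawback is a denominator that varies between PNC visits.
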